3.7.1 Adverse Events and Serious Adverse Events

Adverse events will be coded with MedDRA version 21.0 or later. Analysis of adverse events will include the type, incidence, severity and relationship to study investigational product summarized by MedDRA System Organ Class (SOC) and Preferred Term (PT), by treatment group as well as overall. The AEs summaries will include only treatment-emergent AEs, ie, those starting after the first administration of double-blind investigational product. Subjects will be counted once for specific PT or MedDRA SOC when calculating incidence rates. If the same AE Preferred Term occurs multiple times within a subject, the highest severity and level of relationship observed will be reported. Non-treatment-emergent AEs/serious adverse events (SAEs), ie, those AEs with onset after screening including during the single-blind placebo treatment but before the start of double-blind treatment will be presented in the listings. The percentage of subject with nausea, vomiting and either nausea or vomiting on each day during the dose titration period (Days 17 to 28) will be summarized with the 80% confidence interval. Note that this is not just onset of a new event but includes events where the day is included in the AE start and stop dates. A similar analysis including event rates will be performed for each of the 4-day dose titration period (Days 17-20, 21-24, and 25 to 28) and other dosing periods. Adverse events will be summarized separately for the double-blinded treatment period and for the single-blinded treatment period.

3.7.2 Other Events

3.7.2.1 Hepatic Function Abnormality

Cases where a subject shows elevations in liver biochemistry may require further evaluation and occurrences of aspartate transaminase (AST) or alanine transaminase (ALT) $\geq 3 \times \text{ULN}$ together with total bilirubin $\geq 2 \times \text{ULN}$ may need to be reported as SAEs. Tests for AST, ALT, and total bilirubin must be conducted concurrently, defined as deriving from a single blood draw or from separate blood draws taken within 8 days of each other, and assessed concurrently.

The cases of hepatic function abnormality will be summarized overall, as well as categorized by MedDRA system organ class and preferred term by treatment group.

3.7.2.2 Injection Site Reactions

Treatment-emergent injection site reactions will be summarized overall, as well as categorized by MedDRA system organ class and preferred term by treatment group.

3.7.2.3 Nausea or Vomiting

Treatment-emergent nausea or vomiting events will be summarized overall, as well as categorized by MedDRA system organ class and preferred term by treatment group.

3.7.3 Deaths and Treatment Discontinuations due to Adverse Events

Death and AEs resulting in permanent discontinuation from the study drug will be summarized by treatment. The summary includes overall, categorized by MedDRA system organ class, and preferred term.

3.7.4 Clinical Laboratory Evaluation

Hematology, serum chemistry, and urinalysis laboratory evaluations will be performed during the study. The hematology and serum chemistry (including calcitonin, lipase, and amylase) parameters as well as their changes from baseline and percent changes from baseline will be summarized with descriptive statistics (number of subjects, mean, and standard deviation, median, minimum and maximum) by treatment group. The hematology and serum chemistry results will also be classified as low (below lower limit of reference range), normal (within reference range), or high (above upper limit of reference range). The urinalysis results will be classified as normal or abnormal. The shift from baseline hematology, serum chemistry, and urinalysis results will be summarized by treatment at each evaluation time.

3.7.5 Other Safety Evaluations

3.7.5.1 Vital Signs

Vital signs including pulse rate (beats/min), systolic and diastolic blood pressure (mm Hg), temperature (°C), and respiratory rate (breaths/min), as well as the change from baseline for each of those parameters, will be descriptively summarized by treatment at each time point.

3.7.5.2 Electrocardiogram

Electrocardiogram parameters will be assessed using standard 12-lead electrocardiography. The following Electrocardiogram (ECG) parameters as well as the change from baseline for each of those parameters will be reported and descriptively summarized by treatment group at each of the specified time points: Heart rate (beats/min), RR (msec), PR (msec), QRS (msec), and QT (msec) intervals and the QT corrected interval.

The normality/abnormality of the ECG evaluation will be summarized using frequency tables of the number of subjects with a normal/abnormal ECG evaluation at each scheduled visit.

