4.2.3 Follow-up Period

Table 7 shows all procedures to be conducted during the follow-up period.

Table 7 Schedule of Follow-up Procedures

Study Period	Follow-up Period
Visit Number	Final Visit (V10)
Procedure / Study Day	28 days post last dose (\pm 3 days)
Physical examination (abbreviated)	X
Remove activity monitoring device	X
Weight	X
ECG	X
Vital signs (BP, pulse, body temperature, respiration rate) ^a	X
Serum chemistry panel	X
Calcitonin ^b	X
Haematology	X
Urinalysis	X
HbA1c	X
Urine pregnancy test	X
	
Assessment of TEAEs/TESAEs ^d	X
Concomitant medications ^e	X

ADA = anti-drug antibody; AE = adverse event; BP = blood pressure; ECG = electrocardiogram; HbA1c = glycated haemoglobin, SAE = serious adverse event; TEAE = treatment-emergent adverse event; TESAE = treatment-emergent serious adverse event; ULN = upper limit of normal; V = visit.

^a Blood pressure should be measured once at heart level in the non-dominant arm where possible, with the subject seated and rested for 10 minutes prior to the measurement.

^b Only to be repeated if the calcitonin level was > ULN in the sample taken at the end of dosing.

^c See Section 4.3.7 for details.

^d AEs and SAEs will be assessed from the time of signed informed consent form.

^e If a second non-metformin agent was washed out during the screening period the investigator and/or study team should consider whether it is appropriate to re-start this therapy.

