4.2.4 Early Discontinuation Visit or Unscheduled Study Visit

The following study procedures may be conducted for subjects who prematurely discontinue from the study or for subjects who require an unscheduled study visit. The types of procedures required will be at the discretion of the investigator.

- Targeted physical examination
- ECG

- Vital signs
- Body weight
- [REDACTED]
- Blood tests including chemistry and haematology panel
- [REDACTED]
- Assessment of AEs/serious adverse events (SAEs)
- Concomitant medications
- Urine pregnancy test (if applicable)

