4.3.4.3 Electrocardiograms

At the visits specified in the schedules of study procedures (Table 5, Table 6, and Table 7), ECGs will be obtained after 10 minutes supine rest. Only a single digital ECG recording will be required at the specified time points.

The same recorder will be used for each subject at each time point, if possible. Date and time settings should be checked at the start of each study day and aligned with an official timekeeper for all machines used in the study.

Skin preparation should be thorough and electrode positions should be according to standard 12-lead ECG placement.

In this study lead II or V2 will be analysed and reported as primary. Lead V5 will be analysed, for all visits, as backup for the individual where analysis in lead II or V2 is not deemed possible for pre-dose or significant parts of whole visits or whole visits.

The following variables will be reported: PR, QRS, and QT intervals from the primary lead of the digital 12-lead ECG. The investigator may add extra 12-lead ECG safety assessments if there are any abnormal findings or if the investigator considers it is required for any other safety reason.

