4.3.5 Clinical Laboratory Tests

A Laboratory Manual will be provided to the sites that specifies the procedures for collection, processing, storage, and shipment of samples, as well as laboratory contact information, specific to this clinical research study.

Clinical laboratory safety tests will be performed in a licensed central or licensed local clinical laboratory. Urine pregnancy tests may be performed at the site using a licensed test (dipstick). Abnormal laboratory results should be repeated as soon as possible (preferably within 24 to 48 hours).

The following clinical laboratory tests will be performed (refer to time points in the schedules of study procedures (Section 4.2):

Serum Chemistry

- | | |
|-------------|-------------------|
| • Potassium | • Total bilirubin |
| • Sodium | • Creatinine |
| • ALT | • Blood urea |
| • AST | • Albumin |
| • ALP | |

ALP = alkaline phosphatase; ALT = alanine transaminase; AST = aspartate transaminase.

Notes:

Liver function tests = AST, ALT, ALP, total bilirubin, and albumin

Tests for AST, ALT, ALP, and total bilirubin must be conducted concurrently and assessed concurrently.

Haematology

- White blood cell count with differential
- Red blood cell count
- Haematocrit
- Haemoglobin
- Platelet count
- Mean corpuscular volume
- Mean corpuscular haemoglobin concentration

Urinalysis

- Protein
- Glucose
- Blood
- Urine drug screen ^a
- Ketones

Notes:

Urinalysis for protein, glucose, ketones, and blood may be performed at the site using a licensed test (dipstick).

- ^a Illicit drug panel will test for the following drugs; amphetamines, barbituates, benzodiazepines, cocaine, opiates (morphine, heroin), methamphetamine, cannabinoids (marijuana), methadone, phencyclidine, methylenedioxymethamphetamine (ecstasy), propoxyphene, and tricyclic antidepressants. Subjects who use tricyclic antidepressants or benzodiazepines for an established clinical indication may be permitted to enter the study based upon the judgement of the investigator.

Additional Urine Samples

- Urine samples for DLW assessment
- 24-hour urine collection for protein assessment

Pregnancy Test (females of childbearing potential only)

- Serum human chorionic gonadotropin (hCG; screening if applicable, and Day -1 and 17 only)
- Urine hCG

Other Laboratory/Blood Tests

- Calcitonin
- Alcohol screening test (breath- or urine-based test)
- Pancreatic amylase and lipase
- Glycated haemoglobin
- Anti-drug antibodies (immunogenicity)

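### The SAP's normal/abnormal ECG table has no row for unscheduled or early-discontinuation ECGs, although no ECG is scheduled between Day 17 and Day 59 for a subject who stays on treatment

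*SAP*

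**What the plan says.** SAP 3.7.5.2 plans two ECG outputs. Interval and heart-rate parameters, with changes from baseline, are "descriptively summarized by treatment group at each of the specified time points". The overall reading is shown in "frequency tables of the number of subjects with a normal/abnormal ECG evaluation at each scheduled visit". The section mentions no worst-value or any-post-dose row, and no rule for assigning an unscheduled or early-discontinuation ECG to a visit.

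The protocol provides for ECGs outside the schedule. Section 4.3.4.3 states: "The investigator may add extra 12-lead ECG safety assessments if there are any abnormal findings". Section 4.2.4 lists ECG among the procedures that may be done "for subjects who prematurely discontinue from the study or for subjects who require an unscheduled study visit", and adds: "The types of procedures required will be at the discretion of the investigator".

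Table 6 marks treatment-period ECGs on Day 17 and Day 59 only. Table 7 adds one at V10, timed "28 days post last dose" with a 3-day window either side.

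**The concern.** ECGs are a named secondary safety endpoint (protocol 2.2). Apart from the Day 59 recording, any on-treatment ECG after Day 17 is one that somebody chose to take, often because something looked wrong. The planned table has no place for these recordings. The uncovered stretch includes the rest of the dose titration, which SAP 3.7.1 places on Days 17 to 28.

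If unscheduled or early-discontinuation ECGs are more frequent on MEDI0382 than on placebo, the uncounted abnormalities fall mainly in the MEDI0382 arm and its rate is understated. The documents give no expected rate of either kind of ECG, so this direction is conditional. Early exits are foreseen, however: protocol 4.1.7 allows up to five withdrawn subjects to be replaced.

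**Working it through.** The plan gives no figure for this point, so there is none to reproduce. The check counts scheduled ECGs and follows each kind of recording to the output that would hold it.

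**1. Scheduled ECGs per subject.** Screening (Table 5): 1. Days 17 and 59 (Table 6): 2. V10 (Table 7): 1. Total 1 + 2 + 1 = 4, of which 2 (Day 59 and V10) come after the Day 17 visit.

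**2. The gap for a subject who stays on treatment.** From Day 17 to Day 59 is 59 − 17 = 42 days. The days strictly between are Days 18 to 58, that is 58 − 18 + 1 = 41 days with 0 scheduled ECGs. With a last dose on Day 58, V10 falls on Day 58 + 28 = 86 (83 to 89).

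**3. Subjects who stop early.** V10 = day of last dose + 28, ± 3.
- Last dose Day 25: V10 on Day 53 (50 to 56).
- Last dose Day 42: V10 on Day 70 (67 to 73).

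Protocol 4.1.6 keeps subjects who stop dosing in protocol-specified assessments unless they withdraw consent, are lost to follow-up, start alternative treatment or enter another study. One who stays has 1 scheduled ECG after Day 17, or 2 if Day 59 is also attended. The count is 0 only for a subject who leaves the study before both visits. Protocol 4.1.5 ends all data collection once consent is withdrawn.

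**4. Where each abnormal ECG is reported.**

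| Recording | By-visit ECG table | AE tables | Listing |
|---|---|---|---|
| Day 59 or V10 | Yes | If medically significant or needing intervention | Yes |
| Extra ECG for a finding (4.3.4.3) | No row | Same condition | Yes |
| Early-discontinuation or unscheduled visit (4.2.4) | No row | Same condition | Yes |

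The AE condition is in protocol 5.1, which includes ECG findings among the abnormal findings it covers. The listings are in SAP 3.1. What remains uncounted by arm is an off-schedule abnormal ECG not judged medically significant.

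**5. Size.** One case is 1/16 = 6.3% on MEDI0382 or 1/8 = 12.5% on placebo. Illustration, with assumed inputs: 3 of 16 MEDI0382 subjects leave the study before both Day 59 and V10, one has an abnormal discontinuation ECG, and there are no other abnormalities.
- The Day 59 and V10 rows each show 0/13 = 0%.
- Counting any post-dose ECG gives 1/16 = 6.3% if all three leavers had one.
- It gives 1/14 = 7.1% if only the abnormal case had one, since the discontinuation ECG is discretionary.

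**The case against.** The strongest reply is that little of importance is lost. An arrhythmia or heart block that stops dosing is an adverse event under protocol 4.1.6. It would be counted by arm in the AE tables (SAP 3.7.1) and among discontinuations due to AEs (SAP 3.7.3). Other findings judged medically significant reach the AE tables too, and everything is listed. This stands, and it confines the point to abnormalities below that threshold. It does not remove the point, because a normal/abnormal table exists to count readings whatever the judgement of significance, and a listing gives no rate by arm.

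Second, SAP 3.7.5.2 does not expressly exclude off-schedule ECGs, SAP 3.1 says all available data are included, and templates are left to a statistical programming plan not available here. That also stands in part: the omission is the natural reading of the wording, not a stated exclusion. But the SAP 3.1 sentence concerns imputation, and the counting rule belongs in the SAP.

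Third, the by-visit format follows protocol 4.8.5.2, and a worst-value table has its own bias, because extra ECGs are prompted by findings or by investigator discretion. This is a real limitation. It is why the by-visit table should stay and the number of subjects with unscheduled ECGs should be shown beside the new one.

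**Conclusion.** The point holds as a gap in the ECG summary: off-schedule abnormal ECGs have no row, and a subject who stays on treatment has no scheduled ECG on Days 18 to 58. V10 does not fill the gap, being an off-drug recording. One missed case is 6.3 or 12.5 percentage points; whether any will occur cannot be judged from the documents. Adding the table is an inexpensive improvement to safety reporting.

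A reader might infer more, and the documents do not support it:
- **That anyone stopping before Day 59 contributes nothing after Day 17, so that the table covers completers only.** V10 is a scheduled ECG, and subjects who stop dosing normally stay in follow-up. The inference holds only for those who leave the study before both visits.
- **That every ECG abnormality on Days 18 to 58 must come from an unscheduled ECG.** For an early stopper, V10 can fall in that window, as with a last dose on Day 25.
- **That these findings vanish from all reporting.** AE tables and listings remain.
- **That laboratory results are excluded in the same way.** SAP 3.7.4 says: "The shift from baseline hematology, serum chemistry, and urinalysis results will be summarized by treatment at each evaluation time". That does not expressly exclude unscheduled draws. Chemistry and haematology are also scheduled on Day 32, and SAP 3.7.2.1 summarises hepatic cases separately.

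**What to change.** Keep the by-visit table in SAP 3.7.5.2 and add a baseline-to-worst-post-dose normal/abnormal ECG table by arm, specified as follows:
- **Records:** every ECG after the first double-blind dose, whether scheduled, unscheduled or at early discontinuation.
- **Denominator:** all double-blind-treated subjects with at least one post-dose ECG.
- **Baseline:** the last ECG before the first double-blind dose. This needs stating, because the general definition in SAP 3.1 refers to the first administration of investigational product and could be read as the first single-blind dose.
- **Ascertainment:** the number of subjects per arm with unscheduled ECGs.

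A worst-post-baseline shift for laboratory results is an optional parallel in SAP 3.7.4.

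The cost is a few lines of SAP text and one table from data already collected, with no additional ECG or blood draw. The drawback is that subjects assessed more often have more chances of an abnormal result, so the table should be read with the last item above.

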3.8 Immunogenicity

[REDACTED]

[REDACTED]

[REDACTED]

3.9 Pharmacokinetics

[REDACTED]

3.10 Protocol Deviations

A listing and table of important protocol deviations (IPD) will be provided. The summary of IPD may be prepared by deviation category as well as overall.

4 INTERIM ANALYSIS

No interim analyses are planned.

6 VERSION HISTORY

Version	Date	Summary of Changes	Reason for Change
1.0	10DEC2018	Initial document	Initial document
2.0	23FEB2019	Updates on certain endpoints and analysis populations	Updates needed following protocol amendment
